1. SUMMARY

Rationale: Dementia is a major contributor of dependence and disability in the ageing population and is mainly caused by neurodegenerative and cerebrovascular disease. Vascular cognitive impairment (VCI) occurs in at least 10% of patients who recover from an intracerebral hemorrhage (ICH) and has a major impact on post ICH recovery. In the acute phase of ICH, cognitive impairment may be caused directly by the hemorrhage damaging the brain parenchyma. In the chronic phase, however, further cognitive decline is also prevalent.

Cognitive decline after ICH might be caused by the underlying etiology of the ICH. The most frequent underlying small vessel diseases (SVD) that cause ICH are cerebral amyloid angiopathy (CAA) and hypertensive arteriopathy (HA). CAA and HA have their own radiological signatures of SVD markers which allow for in vivo tracking of disease progression using MRI. Although the initial clinical presentation these two types of SVD differs – CAA classically presents with a lobar ICH, whereas HA causes deep ICH – both groups of patients are at risk of developing dementia. However, it has recently been shown that patients with lobar ICH develop new onset dementia twice as often as patients with deep ICH. Whether underlying CAA pathology causes this increase, remains unclear. In addition, whether ICH accelerates the process of vascular damage and if cognitive decline can be predicted by certain disease markers is uncertain. Understanding the underlying mechanisms for cognitive decline after ICH helps to improve knowledge of prognosis and clinical management of patients who are recovering from ICH.

Objectives: The overall aim of this pilot study is to investigate the development of MRI and CSF markers after CAA-related and HA-related ICH in relation to cognitive decline. The results from this pilot trial will be used to design a larger cohort study to investigate underlying mechanisms of cognitive decline after ICH.

Study design: The study design is a prospective cohort study.

Study population: The study population consists of 32 patients; 16 patients with CAA-related ICH and 16 patients with HA-related ICH who are 55 years or older.

Methods: Data will be collected at four measuring points: at baseline (during hospital admission for the ICH or at the outpatients clinic within one month of presentation with an acute ICH), after three months, after six months and after 12 months. Premorbid cognitive functioning will be assessed with the Informant Questionnaire on Cognitive Decline in the Elderly (IQCODE) to select participants without pre-existing cognitive impairment.

At baseline, the premorbid functional status will be assessed with the modified Rankin Scale (mRS) and Barthell index. A 3Tesla MRI will be performed to assess the most likely underlying cause of the ICH (patients with either CAA or HA-related ICH will be included). Stroke severity will be assessed with the National Institutes of Health Stroke Scale (NIHSS) and a neurologic exam will be performed. Participants will undergo an extensive interview on life-style, vascular risk factors and medication, and

will undergo a blood withdrawal. Neuropsychological testing will be performed and questionnaires will be used for screening for depression, anxiety and psychopathology. In addition, participants will be asked to undergo a lumbar puncture to collect cerebrospinal fluid (CSF).

After three months, neurological examination, and neuropsychological testing will be repeated.

After six and 12 months, the neurological examination, the 3 Tesla MRI and neuropsychological testing will be repeated. Additionally, participants will be asked for a lumbar puncture at these two time points.

Main study parameters/endpoints: The main parameters are cognitive decline (according to the neuropsychological assessment) at 12 months. Secondary outcomes are burden of SVD markers on MRI and CSF markers at baseline, at six months and 12 months.

Nature and extent of the burden and risk associated with participation, benefit and group relatedness: The risks of MRI are minimal (risk of everyday life), because there are no consequences to the health of the participant. Contra-indications will be carefully investigated per subject, burden will be kept at a minimum by using short protocols. There is no direct benefit for the patients except for more insight into the underlying pathophysiology of the hemorrhages related to their disease.

Blood withdrawal and lumbar puncture are routine procedures at the Department of Neurology. Lumbar puncture will be performed by experienced physicians. We will use atraumatic spinal needles to reduce the risk of post-lumbar puncture headache.

Patients will be informed extensively about the potential risks of these procedures, after which written informed consent will be obtained.

2. INTRODUCTION AND RATIONALE

Cognitive impairment after intracerebral hemorrhage

Dementia is a serious public health problem in the ageing population and cerebrovascular disease is a major cause of cognitive decline. After a first stroke, at least 10% of patients without previous cognitive impairment will develop dementia.¹ In a large observational cohort study, even one in three patients develop new onset dementia within five years after stroke.² Even though intracerebral hemorrhage (ICH) and ischemic stroke can both cause vascular cognitive impairment (VCI), ICH has received far less scientific attention than ischemic stroke. Nevertheless, ICH is more strongly associated with new post-stroke dementia than other stroke subtypes.²

Predicting outcome after ICH is challenging. Cognitive decline is believed to cause the greatest impact on quality of life after ICH.³ A certain degree of cognitive deficit in the acute phase of ICH is

likely a direct result of the hemorrhage damaging the brain parenchyma, although it also depends on co-existing neurodegenerative pathology, the hemorrhage volume, and the location of the hemorrhage. Even though these cognitive deficits might partly resolve as the hemorrhage resorbs over time, some of the ICH survivors will have progressive cognitive decline and therefore a poor long-term outcome.³ The ICH might trigger or boost underlying small vessel disease underlying this cognitive decline.

Post-ICH cognitive decline might be caused by the underlying causes of ICH. The most important cause of primary ICH is small vessel disease (SVD).¹ The two most common subtypes of SVD are hypertensive arteriopathy (HA) and sporadic cerebral amyloid angiopathy (CAA). HA results from hypertension-related damage predominantly affecting small perforating end-arteries in the basal ganglia, brain stem, deep white matter, and cerebellum. CAA is caused by β -amyloid deposition within the wall of cortical and leptomeningeal arteries causing pathology in the lobar regions of the brain.⁴ Therefore, when HA leads to an ICH it is most likely located in the deep brain structures, whereas CAA typically causes lobar ICH.⁵

The incidence of new-onset dementia after stroke has been addressed in a cohort of 218 ICH patients. In these ICH survivors without dementia at baseline, new-onset dementia occurred with an incidence of 14.2% at 1 year and 28.3% at 4 years of follow up. Interestingly, this incidence was twice as high in patients with lobar ICH (23.4% at one year follow-up) than for patients with non-lobar ICH (9.2% at one year follow-up). This finding is in line with previous studies linking CAA to cognitive impairment.⁶

MRI markers and cognitive impairment

Underlying SVD-related pathology can be identified using MRI. Even though MRI does not show the entire spectrum of the underlying SVD pathology, it has improved our understanding of SVD pathology extensively in the recent years.⁷ MRI markers associated with CAA often are different or have a different distribution compared with MRI markers associated with HA.⁸ Deep cerebral microbleeds (MB's), white matter hyperintensity (WMH), and MRI visible enlarged perivascular spaces (ePVS) located in the area of the basal ganglia are associated with HA.⁹ Markers associated with CAA include lobar MB's, WMH, ePVS in the subcortical white matter, cortical subarachnoid hemorrhage (cSAH), intragyral hemorrhages, microinfarcts, cortical thinning, and cortical superficial siderosis (cSS).⁴

Severe WMH, lacunar infarcts, microinfarcts, have been associated with vascular cognitive impairment.¹⁰ The association between cognitive impairment and MB's has also been well established,¹¹ and recent studies have shown that cSS plays an important role in predicting progression of CAA.^{12, 13} Additionally, altered white matter integrity measured with diffusion tensor imaging (DTI) has been found in patients with mild cognitive impairment¹⁴ and CAA¹⁵ and might be a marker of cognitive decline in post-ICH patients.

As both HA and CAA are likely to progress over time, and therefore continue to damage the brain, it can be assumed that these two forms of SVD cause further cognitive deterioration after ICH and that this can be demonstrated by progression of the burden of MRI markers.

Biomarkers in cerebrospinal fluid

Although the implications of MRI markers in CAA and HA patients become increasingly clear, it is unknown in what way disease progression and changes in cerebrospinal fluid (CSF) show a correlation. In the hereditary form of CAA, decreasing CSF levels of A β occur before patients develop an ICH, implicating vascular deposition of A β species as early steps in CAA pathogenesis.¹⁶ Whether they have a predictive value, however, for cognitive decline after ICH remains unclear.

Potential risk factors that might affect cognitive decline after ICH

Factors like hyperglycemia, obesity, insulin resistance, and hypertension cause microvascular dysfunction and are therefore associated with cognitive impairment.¹⁷ In order to investigate the effect of SVD on cognition it is important to assess these risk factors, as well as medication use.

Implications on clinical practice

Currently no therapies to prevent or slow down cognitive impairment after stroke exist. However, understanding the underlying cause and the natural disease course might help physicians to inform patients and screen for cognitive decline in patients who are at risk. Furthermore, identifying markers that correlate with cognitive decline might be important for future therapeutic trials. The results of this pilot study will be used to power a larger cohort study to investigate underlying mechanisms of cognitive decline after ICH and the differences between non-CAA and CAA related pathology. We will learn about the prevalence of cognitive decline, the differences between markers and their association with cognitive decline and the optimal time points for MRI (6 or 12 months) to assess the potential of creating a prediction model of the SVD markers and cognitive decline.

Overall aim: The overall aim is to study cognitive decline in patients who recover from ICH and the relation with SVD markers. The results will be used to design a larger cohort study.

3. OBJECTIVES

1. To investigate the proportion of patients with new-onset dementia after HA-related ICH and CAA-related ICH by performing serial follow-up with neuropsychological testing.
2. To investigate MRI markers for SVD disease at baseline and their progression during follow-up and study if and how these markers correlate with cognitive decline after HA-related ICH versus CAA-related ICH.
3. To assess CSF markers at baseline and progression during follow-up and study if and how CSF markers correlate with cognitive decline after HA-related ICH versus CAA-related ICH.
4. To store blood and CSF of CAA and HA patients for biobanking purposes and future research.

The results from this pilot study will be used to design a larger cohort study to investigate underlying mechanisms of cognitive decline after ICH.

The cognitive decline and influencing factors ICH patients will be (whenever appropriate and dependent on the particular research question) compared with data from other research projects in the LUMC like the hereditary form of CAA (HCHWA-D, n=75), sporadic CAA (n=50), Alzheimer's disease, and Huntington's disease or available data on healthy controls.

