5.3 Exclusion criteria

1. Age < 55 y
2. Unable to provide informed consent.
3. Pre-existing cognitive impairment assessed with the Informant Questionnaire on Cognitive Decline in the Elderly (IQCODE); scores between 53 - 63 reflect pre-existing cognitive impairment.¹⁹

4. Contra indications, such as:

Contra-indications for 3T MRI. Examples of possible contra-indications are:

- Claustrophobia
- Pacemakers and defibrillators
- Nerve stimulators
- Intracranial clips
- Intra-orbital or intraocular metallic fragments
- Cochlear implants
- Ferromagnetic implants
- Hydrocephalus pump
- Intra-uterine device
- Permanent make-up
- Tattoos above the shoulders
- Reduced kidney function (estimated GFR < 30 ml/min/1,73m²; or nephrogenic systemic fibrosis / nephrogenic fibrosing nephropathy (NSF/NFD))
- Known prior allergic reaction to gadolinium contrast or one of the constituents of its solution for administration

Contraindications for lumbar puncture:

- Intracranial tumor
- Compressio medullae
- Signs and symptoms of increased intracranial pressure
- Local infections of the skin
- A coagulopathy including use of anti-coagulant drugs (INR ≥ 1.8) or thrombocytopenia (<40)

Use of acetylsalicylic acid, NSAIDs, COX2 inhibitors or prophylactic low-molecular-weight heparin are no contraindications for lumbar puncture,

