6. METHODS

6.1 Study parameters/endpoints

Cognitive functioning

The neuropsychological assessment will consist of a battery of tests that measure different cognitive domains. Premorbid cognitive functioning will be assessed with the Informant Questionnaire on Cognitive Decline in the Elderly (IQCODE). Cognitive functioning will be tested using a Mini-Mental State Examination (MMSE), a Montreal Cognitive Assessment (MOCA), a Frontal Assessment Battery (FAB), Digit Span Test (DST), RAVLT-15 words test, Stroop test, Trail making test, the Hospital Anxiety and Depression Scale (HADS), the Center for Epidemiologic Studies Depression Scale (CES-D), the Neuropsychiatric Inventory Questionnaire (NPI-Q), the Starkstein Apathy Scale (SAS) and the Prikkelbaarheidsschaal (PS). Cognitive impairment was defined as a score ≤ 1.5 standard deviation below the general population mean in one or more cognitive domains.

MRI markers

The presence and number of MBs, cSS, WMH, cSAH, ePVS, microinfarcts, intragyral hemorrhages, cortical atrophy and other new and known small vessel biomarkers will be assessed on 3T and scored according to the STRIVE criteria.²⁰ White matter integrity will be assessed using quantitative MR measurements and perfusion will be assessed.

Biomarkers in blood and CSF

Blood samples will be analyzed for coagulation profiles, cholesterol levels, APOE status, inflammation profile and hormone levels. In addition, extra blood will be stored in the LUMC Biobank sCAA Neurological Diseases for future biomarker studies. Concentrations of A β 40, A β 42, t-tau, and p-tau181 will be measured in CSF and other biomarkers that may be identified in the future.

Other study parameters

Further parameters of this study will include demographic data, current medical conditions, vascular risk factors (including smoking, alcohol use, drugs, physical exercise, sleep, hypertension, hypercholesterolemia, diabetes mellitus, family history and medication; in women also information on female medical history such as number of pregnancies, menstruation cycle and menopause will be retrieved), neurologic history (including previous ischemic or hemorrhagic stroke), BMI, and blood pressure.

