6.2 Study procedures

Data will be collected at four measuring points: at baseline, after three months, after six months and after 12 months:

- **Baseline (during admission or at the outpatient clinic < 1 month after ICH onset)**
Intake, baseline characteristics and neurological examination will be performed, as well as neuropsychological testing, blood sample collection, and a 3Tesla MRI scan. Additionally participants will be asked to undergo a lumbar puncture.
- **Three months (regular follow-up visit)**
At three months during the routine outpatient clinic visit a neurological examination will be performed, as well as neuropsychological testing.
- **Six and twelve months (two additional study visits)**
At six and twelve months, neurological examination will be performed, as well as neuropsychological testing, and a 3Tesla MRI scan. Additionally, participants will be asked to undergo a lumbar puncture.

• Intake, baseline characteristics and neurological examination

During the baseline assessment the following demographic and base line characteristics will be recorded: date of birth, gender, current medical conditions, daily intake alcohol/drugs/caffeine, sleep, physical activity, smoking, medication, cardiovascular risk factors and neurologic history (including previous ischemic or hemorrhagic stroke and history of migraine). In women information about menstruation cycle, pregnancies and menopause will be recorded. BMI will be recorded. Contra-indications for MRI will be checked. A standard neurological examination will be performed.

• Neuropsychological testing

As mentioned in 6.1, cognitive function will be tested using a Mini-Mental State Examination (MMSE), a Montreal Cognitive Assessment (MOCA), a Frontal Assessment Battery (FAB), Digit Span Test (DST), RAVLT-15 words test, Stroop test, Trail making test, the Hospital Anxiety and Depression Scale (HADS), the Center for Epidemiologic Studies Depression Scale (CES-D), the Neuropsychiatric Inventory Questionnaire (NPI-Q), the Starkstein Apathy Scale (SAS) and the Prikkelbaarheidsschaal (PS).

• 3Tesla MRI

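### Objective 1 counts new-onset dementia, but the MMSE decides both dementia and cognitive impairment, and no follow-up visit schedules a measure of daily function or an informant rating that could separate them.

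*Protocol*

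**What the plan says.** Section 3 gives as the first objective: "To investigate the proportion of patients with new-onset dementia after HA-related ICH and CAA-related ICH by performing serial follow-up with neuropsychological testing". Section 8 names new-onset cognitive impairment and dementia as outcomes to compare between the CAA and HA groups, and takes both from the MMSE. It gives no cut-off and nothing that distinguishes one from the other. Section 6.1 has a separate definition of cognitive impairment (1.5 standard deviations below the population mean in at least one domain) but no definition of dementia.

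Daily function appears once, in the Methods part of the Summary: "At baseline, the premorbid functional status will be assessed with the modified Rankin Scale (mRS) and Barthell index". Neither scale is listed in section 6.1 or 6.2. The IQCODE is likewise for premorbid functioning (Summary and 6.1) and serves as an exclusion criterion, where "scores between 53 - 63 reflect pre-existing cognitive impairment" (section 5.3).

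For follow-up, the Summary states: "After three months, neurological examination, and neuropsychological testing will be repeated". Section 6.2 adds: "At six and twelve months, neurological examination will be performed, as well as neuropsychological testing, and a 3Tesla MRI scan", with a lumbar puncture on request. The repeated battery contains cognitive tests together with mood, behaviour, apathy and irritability scales.

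**The concern.** In general clinical usage, dementia is cognitive impairment that costs the patient independence in daily life. The protocol does not state this meaning, but it treats dementia and cognitive impairment as different outcomes, so something must separate them. Nothing scheduled after baseline does.

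Two errors can follow, in opposite directions. The introduction (section 2) says that part of the early cognitive deficit is probably direct damage from the haemorrhage and may partly resolve. A patient with such a focal deficit who remains independent can score low and be counted as demented. Conversely, section 6.3 keeps participants who become mentally incompetent in the study unless they object. They are likely dementia cases and the least likely to complete a test battery, and no structured alternative is planned for them.

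At stake is the first objective. The gap lies in what is collected, so a later analysis plan cannot close it.

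**Working it through.** **Step 1: what is scheduled, and when** (Summary, sections 5.3, 6.1, 6.2 and 8)

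| Element | Baseline | Months 3, 6 and 12 |
|---|---|---|
| mRS, Barthel index | Premorbid status | Not scheduled |
| IQCODE (informant) | Premorbid functioning, for exclusion | Not scheduled |
| Neurological examination | Yes | Yes, at each visit |
| Cognitive tests, including the MMSE | Yes | Yes, at each visit |
| Mood and behaviour scales, including the NPI-Q | Yes | Yes, at each visit |
| Clinical or consensus diagnosis of dementia | None | None |

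The protocol groups the NPI-Q with the mood and behaviour scales and does not present it as a measure of daily function or of cognitive decline. The only stated route to a dementia label is therefore the MMSE rule in section 8, and the same rule yields the label of cognitive impairment.

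**Step 2: the effect of one misclassified patient**

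Input: 16 patients per group (section 5.4). 1/16 = 6.25 percentage points. This is the only size that rests on the protocol's design alone.

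**Step 3: expected number of true cases**

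Inputs: the one-year dementia rates quoted in section 2, 23.4% for lobar and 9.2% for non-lobar ICH, used as stand-ins for the CAA and HA groups.

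- CAA: 16 × 0.234 = 3.7 patients
- HA: 16 × 0.092 = 1.5 patients

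With so few true cases, one false case weighs heavily, most of all in the HA group.

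**Step 4: hypothetical scenarios**

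The protocol gives no misclassification rate, so every value of q, sensitivity and specificity below is assumed.

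(i) Let q be the share of non-demented patients counted as demented, with no true case missed. The apparent rate is p + (1 − p)q. For q = 10%: 0.234 + 0.766 × 0.10 = 31.1%, and 0.092 + 0.908 × 0.10 = 18.3%.

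| q (assumed) | CAA | HA | Ratio |
|---|---|---|---|
| 0 | 23.4% | 9.2% | 2.54 |
| 5% | 27.2% | 13.7% | 1.98 |
| 10% | 31.1% | 18.3% | 1.70 |
| 20% | 38.7% | 27.4% | 1.42 |
| 30% | 46.4% | 36.4% | 1.27 |

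(ii) With sensitivity se and specificity sp, the apparent rate is p·se + (1 − p)(1 − sp), and the false share is (1 − p)(1 − sp) divided by that rate.

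- se 85%, sp 90%: CAA 0.1989 + 0.0766 = 27.5%, false share 28%; HA 0.0782 + 0.0908 = 16.9%, false share 54%.
- se 90%, sp 95%: CAA 0.2106 + 0.0383 = 24.9%, false share 15%; HA 0.0828 + 0.0454 = 12.8%, false share 35%.

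These show the direction (rates rise and the groups look more alike) but do not estimate the error in this trial.

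**The case against.** The strongest reply is that the protocol chose a test-based definition on purpose. Objective 1 says the proportion will come from neuropsychological testing, and section 8 names the MMSE. The choice is consistent in itself, and the need for functional loss comes from outside the document. This stands in part: a rule exists. But one cognitive score without a cut-off serves both states, so the rule cannot give a dementia count distinct from an impairment count.

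A reader might infer four stronger points that the protocol does not support:

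- *Nothing at follow-up could reveal dementia.* A neurological examination takes place at every visit, month 3 is a routine clinic visit, and section 7.2 has adverse events recorded, with lasting disability or incapacity as a seriousness criterion. Severe cases might be noted. What is missing is a standardised measure.
- *The result cannot be compared with the dementia rates in the introduction.* The protocol does not say how that cohort diagnosed dementia, so this cannot be shown either way.
- *The larger study cannot be sized.* The protocol does not say that study will be sized on dementia. Its stated interest is cognitive decline and its mechanisms.
- *A known fraction of counted cases would be false.* The 28% and 54% in step 4 follow entirely from assumed accuracy.

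A further fair point is that the proportion will be imprecise under any definition. With 4 cases in 16, the exact 95% confidence interval is about 7% to 52%. Precise definition will not cure that, but imprecision does not excuse an outcome that cannot be identified.

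**Conclusion.** The concern holds in limited form. Followed as written, the study would label a low cognitive score as dementia. It would have no standardised functional or informant data at 3, 6 or 12 months with which to check that label, and no structured source for patients who cannot be tested. Each misclassified patient shifts a group's proportion by 6.25 points; the number of such patients is unknown.

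The conclusion rests on two premises: that dementia carries its usual meaning of cognition-related loss of independence, and that the visit lists in the Summary and section 6.2 are complete. The damage is confined to objective 1 and the dementia comparison in section 8. The main endpoint is cognitive decline on neuropsychological assessment at 12 months, and objectives 2 and 3 also use cognitive decline; none of these is affected. The point merits an amendment but does not undermine the study as a whole.

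**What to change.** Adopt one of two amendments.

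**(a) Keep the dementia count.** In section 6.2, add the informant IQCODE (with the time before the ICH as reference point), the Barthel index and the mRS at 6 and 12 months, by telephone with the informant if the patient cannot be tested. In section 8, count new-onset dementia only when impairment on the battery goes with informant-confirmed functional decline judged to be due to cognition. That judgement is needed because motor deficit after ICH also worsens the Barthel index and mRS, so a poor score on either is not enough. Report cognitive impairment without functional loss separately. Cost: a short amendment, a brief extra questionnaire for the informant using instruments already in the protocol, and fewer patients counted as demented.

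**(b) Drop the dementia claim.** Restate objective 1 and the matching sentence in section 8 as new-onset cognitive impairment, use the definition in section 6.1 in place of the MMSE rule, and make no statement about dementia. Cost: a change of wording only, but no dementia proportion is reported.

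Option (a) must be in place before the 6-month visits, because function not recorded then cannot be reliably recovered later.
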